4.1 OVERVIEW OF STUDY DESIGN/INTERVENTION

4.2 Design

This is a pilot study with the primary objective to assess the safety of administering the PD-L1 targeting agent durvalumab in combination with recombinant human thyroid stimulating hormone (rhTSH, Thyrogen) stimulated/prepared radioiodine (RAI; ^{131}I) therapy in patients with RAI-avid (RAIA) recurrent and/or metastatic (R/M) thyroid cancer. If >1 of the first 3 patients or >2 of the first 6 patients develop a DLT related to durvalumab, further accrual to the study will be halted. If this threshold is not crossed, 11 patients in total will be accrued to the pilot study. All adverse events will be graded according to CTCAE v4.00. Secondary objectives are assessing best overall response (BOR) and progression-free survival (PFS) RECIST v1.1 criteria.

4.3 Intervention

Enrolled patients will be treated with durvalumab 1500 mg IV approximately every 4 weeks. In Cycle 1/Week 3, Thyrogen 0.9 mg IM will be administered on two consecutive calendar days followed by 100 mCi (+/- 10 mCi) of RAI the next calendar day. Durvalumab will be continued approximately every 4 weeks. Only adverse events occurring within 6 weeks of the first durvalumab dose will be counted as dose limiting toxicities (DLTs). Tumor assessments according to RECIST v1.1 criteria will be conducted with serial radiologic imaging at baseline and approximately every 2 cycles of durvalumab therapy (or every 8 weeks +/- 1 week). After 6 months of treatment, imaging will be obtained every 3 cycles (or every 12 weeks (+/- 1 week)). Patients will remain on durvalumab treatment until there is confirmed progression of disease, unacceptable toxicity, withdrawal of consent, or if the study physician feels removal from the study is in the patient's best interest. One exception to these discontinuation rules: given the potential for delayed responses following short periods of disease progression with immunotherapy, subjects may continue to receive therapy beyond radiographic progression if the investigator concludes that the subject is tolerating study drug and continued therapy may provide clinical benefit. Adverse events will be monitored from the time informed consent is signed until 90 days after the last dose of drug. It is mandatory that patients agree to undergo two research biopsies, which will be analyzed to evaluate how this experimental approach changes the genomic/transcriptomic landscape of the tumor and the tumor immune infiltrate (exemption from the second biopsy may be considered if after performance of the first biopsy it is felt that a subsequent biopsy is not reasonably safe for the patient). Archival tumor tissue and serial peripheral blood collections will also be analyzed for potential biologic correlates of immune activation and efficacy derived from the combination therapy.

5.1 THERAPEUTIC/DIAGNOSTIC AGENTS

5.2 Durvalumab

The Investigational Products Supply section of AstraZeneca/MedImmune will supply durvalumab to the investigator as a 500-mg vial solution for infusion after dilution. Durvalumab is an IND agent that is not FDA-approved for any indication.

Formulation/packaging/storage

Durvalumab will be supplied by AstraZeneca as a 500-mg vial solution for infusion after dilution. The solution contains 50 mg/mL durvalumab, 26 mM histidine/histidine-hydrochloride, 275 mM trehalose dihydrate, and 0.02% (weight/volume) polysorbate 80; it has a pH of 6.0. The nominal fill volume is 10 mL. Investigational product vials are stored at 2°C to 8°C (36°F to 46°F) and must not be frozen. Durvalumab must be used within the individually assigned expiry date on the label.

Durvalumab Doses and treatment regimens

Durvalumab will be administered 1500 mg IV approximately every 4 weeks. Two weeks after the first dose and prior to the second dose of durvalumab, Thyrogen and RAI will be administered. Durvalumab will be continued approximately every 4 weeks. Patients will remain on durvalumab until there is confirmed progression of disease, unacceptable toxicity, withdrawal of consent, or if the study physician feels removal from the study is in the patient's best interest. One exception to these discontinuation rules: given the potential for delayed responses following short periods of disease progression with immunotherapy, subjects may continue to receive therapy beyond radiographic progression if the investigator concludes that the subject is tolerating study drug and continued therapy may provide clinical benefit.

Study drug preparation

For patients weighing \geq 30 kg, a fixed dose of 1500 mg Q4W durvalumab (equivalent to 20 mg/kg Q4W) (based on an average body WT of 75 kg) should be prepared. For subjects <30 kg body weight, dose is determined using body mass, calculating the stock volume of durvalumab to achieve the accurate dose according to Appendix 2.

Preparation of durvalumab doses for administration with an IV bag

The dose of durvalumab for administration must be prepared by the Investigator's or site's designated IP manager using aseptic technique. Total time from needle puncture of the durvalumab vial to the start of administration should not exceed:

- 24 hours at 2°C to 8°C (36°F to 46°F)
- 4 hours at room temperature

If in-use storage time exceeds these limits, a new dose must be prepared from new vials. Infusion solutions must be allowed to equilibrate to room temperature prior to commencement of administration.

No incompatibilities between durvalumab and polyvinylchloride or polyolefin IV bags have been observed. Dose of 1500 mg durvalumab for patients >30 kg will be administered using an IV bag containing 0.9% (w/v) saline with a final durvalumab concentration ranging from 1 to 20 mg/mL, and delivered through an IV administration set with a 0.2- or 0.22- μ m in-line filter.

Remove a volume of IV solution from the IV bag equal to the calculated volume of durvalumab to be added to the IV bag prior to addition of durvalumab. Next, the volume of durvalumab (i.e., 15.0 mL for 750 mg or 30.0 mL for 1500 mg of durvalumab) is added to the IV bag such that final concentration is within 1 to 20 mg/mL (IV bag volumes 100 to 1000 mL). Mix the bag by gently inverting to ensure homogeneity of the dose in the bag.

Patient weight at baseline should be used for dosing calculations in patients \leq 30 kg unless there is a \geq 10% change in weight. Dosing day weight can be used for dosing calculations instead of baseline weight per institutional standard.

For patients <30kg, calculate the dose volume of durvalumab and number of vials needed for the subject to achieve the accurate dose according to Appendix 2.

Durvalumab will be administered at room temperature (approximately 25°C) by controlled infusion via an infusion pump into a peripheral or central vein. Following preparation of durvalumab, the entire contents of the IV bag should be administered as an IV infusion over approximately 60 minutes (\pm 5 minutes), using a 0.2, or 0.22- μ m in-line filter. Less than 55 minutes is considered a deviation.

The IV line will be flushed with a volume of IV solution (0.9% [w/v] saline) equal to the priming volume of the infusion set used after the contents of the IV bag are fully administered, or complete the infusion according to institutional policy to ensure the full dose is administered and document if the line was not flushed.

Standard infusion time is 1 hour. However, if there are interruptions during infusion, the total allowed time should not exceed 8 hours at room temperature. The table below summarizes time allowances and temperatures.

Durvalumab hold and infusion times

Maximum time from needle puncture to start of administration	4 hours at room temperature, 24 hours at 2°C to 8°C
Maximum time for IV bag infusion, including interruptions	8 hours at room temperature

In the event that either preparation time or infusion time exceeds the time limits outlined above, a new dose must be prepared from new vials. Durvalumab does not contain preservatives, and any unused portion must be discarded.

Monitoring of dose administration

Subjects will be monitored before, during and after the infusion with assessment of vital signs at the times specified in the Schedule of Assessment. Subjects are monitored (pulse rate, blood pressure)

approximately every 30 minutes during the infusion period (including times where infusion rate is slowed or temporarily stopped).

In the event of a ≤Grade 2 infusion-related reaction, the infusion rate of study drug maybe decreased by 50% or interrupted until resolution of the event (up to 4 hours) and re-initiated at 50% of the initial rate until completion of the infusion. For subjects with a ≤Grade 2 infusion-related reaction, subsequent infusions may be administered at 50% of the initial rate. Acetaminophen and/or an antihistamine (e.g., diphenhydramine) or equivalent medications per institutional standard may be administered at the discretion of the investigator. If the infusion-related reaction is Grade 3 or higher in severity, study drug will be discontinued. The standard infusion time is one hour, however if there are interruptions during infusion, the total allowed time from infusion start to completion of infusion should not exceed 4 hours at room temperature, with maximum total time at room temperature not exceeding 4 hours (otherwise requires new infusion preparation).

As with any antibody, allergic reactions to dose administration are possible.

5.2 Thyrotropin alpha (Thyrogen; Genzyme)

Thyrogen will be given as 0.9 mg IM daily injections administered for two consecutive days prior to RAI. The Thyrogen will be administered in clinic.

5.3 ^{131}I (RAI; sodium iodide; I-131)

100 mCi (+/- 10 mCi) of ^{131}I will be administered a day after Thyrogen injections have been administered for two consecutive calendar days. This is a low, empiric ^{131}I activity recommended for the treatment of loco-regional or metastatic RAI-avid thyroid cancer, even in patient populations at increased risk of ^{131}I therapy (elderly, patients with renal insufficiency)³¹. ^{131}I has a half-life of 8 days and relatively high principal photon energy of 364 keV accompanied by beta particle emissions. It is administered orally in the form of capsules or liquid. Pregnancy and breastfeeding are contraindications to radioiodine treatment. A beta-HCG pregnancy test must be performed up to 2 days prior to the administration of ^{131}I (for woman of child-bearing potential). ^{131}I is an FDA-approved agent for the treatment of thyroid cancer. The ^{131}I will be administered in clinic.

6.1 CRITERIA FOR SUBJECT ELIGIBILITY

The protocol will enroll patients with RAI-avid recurrent/metastatic thyroid cancer.

6.2 Subject Inclusion Criteria

- Patients must have histologically or cytologically confirmed thyroid carcinoma of follicular origin (including papillary, follicular, hurthle cell or poorly differentiated subtypes and their respective variants).
- Diagnosis of recurrent and/or metastatic thyroid cancer.
- At least one RAI-avid lesion identified on the most recent radioiodine scan (a diagnostic, post-therapy, or post-ablation scan) **OR** at least one lesion on the most recent FDG PET scan with an SUVmax of 10 or less. (Both RAI-sensitive and RAI-refractory patients are eligible if at least one tumor with RAI avidity of any degree can be identified within one of these parameters.)

- Patients must have measurable disease, defined as at least one lesion that can be accurately measured in at least one dimension (longest diameter to be recorded for non-nodal lesions and short axis for nodal lesions) as ≥ 20 mm with conventional techniques or as ≥ 10 mm with CT scan, MRI, or calipers by clinical exam. See Section 12 for the evaluation of measurable disease. Tumors in previously irradiated fields may be considered measurable if there is evidence of tumor progression after radiation treatment.
- ECOG Performance Status (PS) 0 or 1. (or Karnofsky $\geq 60\%$)
- Age ≥ 18 years at time of study entry
- Adequate normal organ and marrow function as defined below:
 - Hemoglobin ≥ 9.0 g/dL
 - Absolute neutrophil count (ANC) $\geq 1.5 \times 10^9/L$ (≥ 1500 per mm 3)
 - Platelet count $\geq 100 \times 10^9/L$ ($\geq 100,000$ per mm 3)
 - Serum bilirubin $\leq 1.5 \times$ institutional upper limit of normal (ULN). (This will not apply to subjects with confirmed Gilbert's syndrome (persistent or recurrent hyperbilirubinemia that is predominantly unconjugated in the absence of hemolysis or hepatic pathology), who will be allowed only in consultation with their physician.)
 - AST (SGOT)/ALT (SGPT) $\leq 2.5 \times$ institutional upper limit of normal unless liver metastases are present, in which case it must be ≤ 5 times ULN
 - Serum creatinine CL >40 mL/min by the Cockcroft-Gault formula (Cockcroft and Gault 1976) or by 24-hour urine collection for determination of creatinine clearance:

Males:

$$\text{Creatinine CL (mL/min)} = \frac{\text{Weight (kg)} \times (140 - \text{Age})}{72 \times \text{serum creatinine (mg/dL)}}.$$

Females:

$$\text{Creatinine CL (mL/min)} = \frac{\text{Weight (kg)} \times (140 - \text{Age})}{72 \times \text{serum creatinine (mg/dL)}} \times 0.85$$

- Female subjects must either be of non-reproductive potential (i.e., post-menopausal by history: ≥ 60 years old and no menses for ≥ 1 year without an alternative medical cause; OR history of hysterectomy, OR history of bilateral tubal ligation, OR history of bilateral oophorectomy) or must have a negative serum pregnancy test upon study entry.
- Subject is willing and able to comply with the protocol for the duration of the study including undergoing treatment and scheduled visits and examinations including follow up.
- Patients must agree to undergo two research biopsies of (a) malignant lesion(s). Biopsies do not need to be done if the investigator or person performing the biopsy judges there is no tumor accessible for biopsy, the only accessible tumor must be used for RECIST measurement, or the biopsy poses too great a risk to the patient. . If the patient has only one RECIST measurable target lesion for response assessment, research biopsies must not be performed on that target lesion.
- Availability of archival tumor tissue from the thyroid cancer primary or metastasis (a tissue block or a minimum of 30 unstained slides would be required. Patients with less archival tissue available may still be eligible for the study after discussion with the MSK Principal Investigator.)

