12.1 Disease Parameters

Measurable disease. Measurable lesions are defined as those that can be accurately measured in at least one dimension (longest diameter to be recorded) as ≥ 20 mm by chest x-ray, as ≥ 10 mm with CT scan, or ≥ 10 mm with calipers by clinical exam. All tumor measurements must be recorded in millimeters (or decimal fractions of centimeters).

Note: Tumor lesions that are situated in a previously irradiated area are not considered measurable unless there has been demonstrated progression in the lesion.

Malignant lymph nodes. To be considered pathologically enlarged and measurable, a lymph node must be ≥ 15 mm in short axis when assessed by CT scan (CT scan slice thickness recommended to be no greater than 5 mm). At baseline and in follow-up, only the short axis will be measured and followed.

Non-measurable disease. All other lesions (or sites of disease), including small lesions (longest diameter <10 mm or pathological lymph nodes with ≥ 10 to <15 mm short axis), are considered non-measurable disease. Bone lesions, leptomeningeal disease, ascites, pleural/pericardial effusions, lymphangitis cutis/pulmonitis, inflammatory breast disease, and abdominal masses (not followed by CT or MRI), are considered as non-measurable.

Note: Cystic lesions that meet the criteria for radiographically defined simple cysts should not be considered as malignant lesions (neither measurable nor non-measurable) since they are, by definition, simple cysts.

'Cystic lesions' thought to represent cystic metastases can be considered as measurable lesions, if they meet the definition of measurability described above. However, if non-cystic lesions are present in the same patient, these are preferred for selection as target lesions.

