12.2 Methods for Evaluation of Measurable Disease

All measurements should be taken and recorded in metric notation using a ruler or calipers. All baseline evaluations should be performed as closely as possible to the beginning of treatment and never more than 4 weeks before the beginning of the treatment.

The same method of assessment and the same technique should be used to characterize each identified and reported lesion at baseline and during follow-up. Imaging-based evaluation is preferred to evaluation by clinical examination unless the lesion(s) being followed cannot be imaged but are assessable by clinical exam.

Clinical lesions: Clinical lesions will only be considered measurable when they are superficial (e.g., skin nodules and palpable lymph nodes) and ≥ 10 mm diameter as assessed using calipers (e.g., skin nodules). In the case of skin lesions, documentation by color photography, including a ruler to estimate the size of the lesion, is recommended.

Chest x-ray: Lesions on chest x-ray are acceptable as measurable lesions when they are clearly defined and surrounded by aerated lung. However, CT is preferable.

Conventional CT and MRI This guideline has defined measurability of lesions on CT scan based on the assumption that CT slice thickness is 5 mm or less. If CT scans have slice thickness greater than 5 mm, the minimum size for a measurable lesion should be twice the slice thickness. MRI is also acceptable in certain situations (e.g. for body scans).

Use of MRI remains a complex issue. MRI has excellent contrast, spatial, and temporal resolution; however, there are many image acquisition variables involved in MRI, which greatly impact image quality, lesion conspicuity, and measurement. Furthermore, the availability of MRI is variable globally. As with CT, if an MRI is performed, the technical specifications of the scanning sequences used should be optimized for the evaluation of the type and site of disease. Furthermore, as with CT, the modality used at follow-up should be the same as was used at baseline and the lesions should be measured/assessed on the same pulse sequence. It is beyond the scope of the RECIST guidelines to prescribe specific MRI pulse sequence parameters for all scanners, body parts, and diseases. Ideally, the same type of scanner should be used and the image acquisition protocol should be followed as closely as possible to prior scans. Body scans should be performed with breath-hold scanning techniques, if possible.

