12.4 Response Criteria

12.4.1 Evaluation of Target Lesions

Complete Response (CR): Disappearance of all target lesions. Any pathological lymph nodes (whether target or non-target) must have reduction in short axis to <10 mm.

Partial Response (PR): At least a 30% decrease in the sum of the diameters of target lesions, taking as reference the baseline sum diameters.

Progressive Disease (PD): At least a 20% increase in the sum of the diameters of target lesions, taking as reference the smallest sum on study (this includes the baseline sum if that is the smallest on study). In addition to the relative increase of 20%, the sum must also demonstrate an absolute increase of at least 5 mm. (Note: the appearance of one or more new lesions is also considered progressions).

Stable Disease (SD): Neither sufficient shrinkage to qualify for PR nor sufficient increase to qualify for PD, taking as reference the smallest sum diameters while on study.

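### Section 6.2 accepts lymph nodes of 10 mm short axis as measurable for entry, while Section 12.1 classes nodes of 10 to <15 mm as non-measurable

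*Combined protocol and SAP*

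**What the plan says.** Section 6.2 makes measurable disease an entry requirement and supplies its own definition. It says that nodes are measured by short axis and then gives nodal and non-nodal lesions the same limits: "short axis for nodal lesions) as ≥ 20 mm with conventional techniques or as ≥ 10 mm with CT scan, MRI, or calipers". It then points to Section 12 for evaluation of measurable disease, without saying which section governs if they differ.

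Section 12.1 sets a separate nodal rule: "a lymph node must be ≥ 15 mm in short axis when assessed by CT scan". Its definition of non-measurable disease includes "pathological lymph nodes with ≥ 10 to <15 mm short axis), are considered non-measurable disease".

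Section 12.2, on clinical lesions, speaks of lesions that are "superficial (e.g., skin nodules and palpable lymph nodes) and ≥ 10 mm diameter as assessed using calipers". It names palpable nodes, uses diameter, and does not repeat the short-axis rule.

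Section 12.1 draws target lesions only from measurable lesions. Section 12.4.3 has one response table for patients with target disease and another for patients without; the second offers CR, Non-CR/non-PD, not evaluated and PD. Section 14.0 defines BOR as CRs plus PRs.

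**The concern.** The entry rule and the response rules use different definitions of a measurable node. Because Section 6.2 names the nodal short axis explicitly, its 10 mm limit cannot be read as meant for non-nodal lesions only. Section 15.2 has staff confirm eligibility on a checklist tied to the inclusion and exclusion criteria, so a checklist built from Section 6.2 would admit a patient whom Section 12 treats as having no measurable disease.

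What is at stake is the two secondary endpoints. Such a patient counts towards BOR but cannot be assigned a PR. For PFS, progression in the existing nodes would rest on unequivocal non-target progression and not on the measured rule (20% and 5 mm). There is also a side effect within Section 6.2: it bars research biopsy of a sole measurable target lesion, and whether a lone 12 mm node has that protection depends on which section is followed.

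**Working it through.** The plan gives no figure for this point, so the check sets the rules side by side and follows one patient through them.

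1. **Zone of conflict.** Imaged nodal short axis from 10 mm to <15 mm: measurable under 6.2, non-measurable under 12.1.

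2. **Path under the text as written.** Nodes of 10 to <15 mm only → meets 6.2 → non-measurable (12.1) → no target lesion (12.1) → non-measurable table (12.4.3) → no PR category → can be a responder for BOR (14.0) only through CR.

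3. **When the missing PR category matters.** Section 12.4.1 defines PR as "At least a 30% decrease in the sum of the diameters of target lesions, taking as reference the baseline sum diameters", and for CR says "Any pathological lymph nodes (whether target or non-target) must have reduction in short axis to <10 mm". Section 12.4.2 uses the same <10 mm limit for non-target nodes. Take a lone node of baseline size *b* with normal markers and no other disease. PR as a target would need a size of at most 0.7*b*, and 0.7*b* < 10 whenever *b* < 10/0.7 = 14.3 mm. Below 14.3 mm, any node that shrinks enough for PR is therefore already a CR under either rule, and BOR does not differ. From 14.3 to <15 mm the gap is under 0.5 mm wide (0.7 × 15 = 10.5 mm against 10 mm). Example: 14.8 to 10.2 mm is (10.2 − 14.8)/14.8 = −31.1%.

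4. **Several nodes.** Two 14 mm nodes reaching 5 and 11 mm: the sum goes from 28 to 16 mm, and (16 − 28)/28 = −42.9%. If the 6.2 limit were carried into target selection, this is PR. Under Section 12 as written one node is still ≥10 mm, so it is Non-CR/non-PD.

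5. **PFS.** For target lesions, progression needs a 20% increase from the smallest sum, and "the sum must also demonstrate an absolute increase of at least 5 mm". If a lone 12 mm node were a target and 12 mm its smallest size, progression would be reached at 12 + max(0.2 × 12, 5) = 17 mm. As a non-target there is no size threshold. New lesions count as progression either way.

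6. **Size for BOR.** Assuming a denominator of 11, one reclassified patient is worth 1/11 = 9.1 points. For example, 1/11 = 9.1% (exact 95% CI 0.2 to 41.3%) becomes 2/11 = 18.2% (2.3 to 51.8%).

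7. **Primary design.** The stopping rule in Section 14.0 (more than 1 of 3, more than 2 of 6, more than 2 of 11) depends only on DLT counts. Exact binomial enumeration gives 0.1012 at a DLT rate of 0.10 and 0.8075 at 0.35, matching the stated type I error and power. Nodal size does not enter.

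**The case against.** The strongest reply is that Section 12 already settles the scoring. Section 6.2 decides entry and does not assign target lesions. Section 12.1 does that, and Section 12.4.3 has a table for patients without target disease. Section 6.2 also refers the reader to Section 12, and the protocol adopts RECIST 1.1 throughout. Much of this stands. It means that the differences in steps 4 and 5 arise only if someone carries the 6.2 limit into target-lesion selection. It does not remove the conflict at entry, because the cross-reference sets no precedence over the explicit 10 mm.

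A reader might go further and infer that slight nodal shrinkage would be counted as response. For example, a 12 mm node reaching 9.9 mm (−17.5%) while a tumor marker stays raised would be target CR with non-target Non-CR/Non-PD, hence PR. The documents do not support this as the planned result. Section 12 makes that node a non-target. Section 12 does not name thyroglobulin or any other thyroid marker as the one that must normalize. Section 10.1 asks for objective responses to be confirmed at least 4 weeks later.

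Nor can one say that every patient with nodes of 10 to <15 mm lacks a target lesion. The caliper wording in Section 12.2 leaves superficial palpable nodes unclear, so the statement is limited to imaged nodes.

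Finally, BOR is a secondary estimate in 11 patients with no hypothesis test, and the two intervals in the working overlap widely. That is a fair argument for treating the point as minor.

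**Conclusion.** The contradiction is real but small. Followed as written, Section 6.2 can admit a patient with imaged nodes of 10 to <15 mm as having measurable disease, and Section 12 then gives that patient no target lesion and no PR category. Only BOR and PFS are touched. The effect on BOR is at most 9.1 percentage points per affected patient, assuming that all 11 patients form the denominator. It is nil for a lone node below 14.3 mm with normal markers and no other disease. The documents do not say how many such patients to expect; there may be none. Nothing here bears on the DLT endpoint, the stopping rule or the sample size.

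**What to change.** - **Section 6.2:** add that lymph nodes qualify as measurable only if the short axis is 15 mm or more, as defined in Section 12.1. Leave the non-nodal limits as they are.
- **Modalities:** use the same imaging modalities for nodes in 6.2 and 12.1. Section 6.2 lists MRI and the 12.1 nodal rule names only CT; align them without removing MRI.
- **Section 12.2:** state that palpable nodes must also meet the 12.1 short-axis rule.
- **Eligibility checklist:** update it to match.
- **Patients already enrolled on nodes of 10 to <15 mm alone:** score them by the non-measurable table in 12.4.3, as Section 12 already implies.

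The drafting cost is a few sentences and a checklist change. The real cost is accrual: patients whose only measurable disease is such nodes become ineligible. At the roughly 1 patient per month expected in Section 14.0, each exclusion costs about a month. Patients with a qualifying non-nodal lesion are unaffected.

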8.1 PRETREATMENT EVALUATION

Within 4 weeks of starting on study, the following tests/evaluations need to be done:

- Signing the Informed Consent Form.
- History and Physical Examination.
- Vital signs (pulse, blood pressure), including weight.
- Performance Status (Eastern Cooperative Oncology Group (ECOG) or Karnofsky Performance Status (KPS)) designation.
- Electrocardiogram (ECG or EKG) in triplicate.
- Radiology studies (CT(s) without contrast and/or MRI(s)) for disease assessment).
- Recording concurrent medications.

- Confirm availability of archival tumor tissue (if tissue is not already available at MSK, physical receipt of tissue is not required for study enrollment or initiation).
- Research tumor biopsy: The research biopsy will be performed any time prior to Week 1 Day 1 (can completed > 4 weeks before starting on study). Radiologic guidance (CT, MRI or ultrasound guided) approaches and obtaining multiple cores to ensure sufficient biopsy material (at least 3 cores preferred) are allowed as long as it is considered safe for the patient (image-guided biopsies will be performed by a radiology physician with the appropriate expertise).
- Research blood draw: Any time prior to start of study, approximately 10 mL of blood, preferably in a lavender top tube (with EDTA).
- Hematology tests (see Section 10).
- Clinical chemistry tests (see Section 10).
- Urinalysis (see Section 10).
- Pregnancy test in women of child-bearing potential (serum or urine beta-hCG within 7 days of starting the study).

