14.0 BIOSTATISTICS

The primary objective of this pilot study will be to assess the safety of administering durvalumab in combination with Thyrogen-stimulated RAI therapy in patients with recurrent/metastatic thyroid cancer. The period of dose limiting toxicity (DLT) monitoring will be 6 weeks beginning from the first durvalumab dose. Definitions for DLT are in Section 9.3. Subjects who are removed from the study for reasons other than DLT prior to the administration of the first Thyrogen injection will be replaced with another subject. Patients who do not complete the 6 week period of monitoring beginning from the first durvalumab dose for reasons other than DLT will also be replaced. If >1 of the first 3 patients, or >2 of the first 6 patients, develop DLT related to durvalumab, further accrual to the study will be halted. If this rule is not met, we plan to accrue 11 patients in total to this pilot study (see table below). All toxicities will be graded according to CTCAE v4.0.

Number of DLTs to stop in first 3 patients	Number of DLTs to stop in first 6 patients	Number of DLTs to stop in all 11 patients	Acceptable toxicity rate (H0)	Unacceptable toxicity rate (H1)	Type I error rate	Power
>1	>2	>2	0.10	0.35	0.101184466	0.80748277

Secondary objectives will be determining the best overall response rate (BOR; CRs plus PRs per RECIST v1.1 criteria) and progression-free survival (estimated using Kaplan-Meier methodology with time origin at the start of the treatment; PFS). For PFS, patients will be followed until progression of disease or death, whichever come first. Patients who continue treatment beyond initial investigator-assessed, RECIST 1.1-defined progression, and are subsequently removed from study within the

next radiographic assessment for progression, will be considered to have investigator-assessed progressive disease at the time of the initial progression event.

Exploratory objectives:

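### Section 6.2 joins ECOG 0-1 and Karnofsky ≥60% with no conversion or governing scale, so the Karnofsky route can admit patients the ECOG limit excludes, and they count in the DLT assessment

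*Combined protocol and SAP*

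**What the plan says.** Section 6.2 (Subject Inclusion Criteria) gives the criterion as "ECOG Performance Status (PS) 0 or 1. (or Karnofsky" ≥60%). The two limits are alternatives.

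Section 8.1 (Pretreatment Evaluation) asks for "Performance Status (Eastern Cooperative Oncology Group (ECOG) or Karnofsky Performance Status (KPS)) designation", so either scale may be recorded. The calendar in Section 10.1 lists performance status without naming a scale.

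Section 14.0 (Biostatistics) sets the safety rule. Accrual halts "If >1 of the first 3 patients, or >2 of the first 6 patients, develop DLT related to durvalumab". The table adds a limit of more than 2 under "Number of DLTs to stop in all 11 patients". Otherwise, "we plan to accrue 11 patients in total to this pilot study". Two groups are replaced: patients removed before the first Thyrogen injection for non-DLT reasons, and patients who do not finish the 6-week window ("for reasons other than DLT will also be replaced"). Neither provision refers to performance status.

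**The concern.** An inclusion criterion that offers two scales should describe one population on both. Here the limits sit side by side without a conversion, and no section says which prevails if they disagree. If Karnofsky 60 is a worse state than ECOG 1, the same patient fails the first limit and passes the second, and the broader limit decides entry.

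What is at stake is the definition of the safety population. Safety is the primary objective, the cohort is 11 patients, and one patient is a third of the first look. If patients with poorer performance status have more Grade 3 or higher events, their entry could move the DLT count for reasons unconnected with the combination. If only Karnofsky is recorded for some patients, the report also could not state the cohort's ECOG distribution.

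**Working it through.** **1. Do the two limits agree?** The documents contain no conversion, so this step needs an assumption. Two pairings in common use set ECOG 1 equal to Karnofsky 70-80 or to Karnofsky 80-90. Under either, a score of 60 lies below ECOG 1. Only a conversion that places 60 within ECOG 1 would make the limits agree, and the protocol prints none.

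**2. Does such a patient count?** Yes. The replacement provisions in Sections 9.4 and 14.0 cover only the two non-DLT situations described above. A patient admitted by the Karnofsky route who completes 6 weeks, or has a DLT, counts at 3, at 6 and at 11.

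**3. Are the stated operating characteristics affected?** Inputs from the Section 14.0 table: stop if more than 1 of 3, more than 2 of 6 or more than 2 of 11; acceptable rate 0.10; unacceptable rate 0.35. At a rate of 0.10:

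- Look at 3: 3(0.01)(0.9) + 0.001 = 0.0280.
- Look at 6, not already stopped: one DLT in the first three, then at least two in the next three, plus none and then three: 0.243 × 0.028 + 0.729 × 0.001 = 0.0075.
- Look at 11, not already stopped. The chances of carrying 0, 1 or 2 DLTs forward from six patients are 0.531441, 0.354294 and 0.078732. The chances of at least 3, 2 or 1 DLTs in the last five are 0.00856, 0.08146 and 0.40951. The sum of products is 0.0657.
- Total: 0.0280 + 0.0075 + 0.0657 = 0.1012, against 0.101184466 stated.

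At 0.35 the same enumeration gives 0.2818 + 0.1368 + 0.3890, or 0.8075 before rounding of the terms, against 0.80748277 stated. Both figures reproduce. They are computed at fixed DLT rates, so the eligibility wording does not enter.

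**4. Illustration of the possible effect on stopping.** The documents give no DLT rate by performance status, so every rate q below is assumed. The remaining patients are held at 0.10. With one Karnofsky-route patient among the first three, the chance of more than 1 DLT in 3 is q(1 − 0.81) + (1 − q)(0.01) = 0.01 + 0.18q. With all three at rate q it is 3q²(1 − q) + q³. The last two columns come from the same exact enumeration.

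| Karnofsky-route patients in first three | Assumed q | Stop at 3 | Stop at 3 or 6 | Cross any of the three limits |
|---|---|---|---|---|
| 0 | – | 0.0280 | 0.0355 | 0.1012 |
| 1 | 0.15 | 0.0370 | 0.0454 | 0.1145 |
| 1 | 0.20 | 0.0460 | 0.0552 | 0.1279 |
| 1 | 0.30 | 0.0640 | 0.0749 | 0.1546 |
| 3 | 0.20 | 0.1040 | 0.1153 | 0.1953 |
| 3 | 0.35 | 0.2818 | 0.2944 | 0.3751 |

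If q = 0.10, every row returns to the first.

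**The case against.** The strongest objection is that the mapping comes from outside the documents. No section converts ECOG to Karnofsky, and the sponsor may have meant Karnofsky ≥60% as a deliberately broader alternative. This limits the claim to what the route *can* admit, under a stated assumption. It does not remove the point: with no mapping at all, the criterion still has two thresholds, no conversion and no governing scale.

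A second objection is that other criteria already restrict frail patients. Section 6.2 sets organ-function limits. Section 6.3 excludes uncontrolled intercurrent illness and any condition that the investigator thinks would interfere with interpreting safety. These narrow entry but do not reconcile the scales.

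A third is that DLTs must generally be at least possibly related to durvalumab, and that Section 9.4 excludes toxicity clearly due to the disease or another cause. This weakens the step from poor performance status to DLTs without closing it. Possible relatedness is a low bar, and the sentence in 9.4 that counts any event requiring durvalumab discontinuation does not mention relatedness.

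Several stronger readings are tempting but unsupported:

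- A reader might infer that the type I error or power is wrong. Both reproduce.
- A reader might take the illustrated probabilities as the size of a bias. They rest on assumed rates, and nothing indicates how many Karnofsky-60 patients would enrol.
- A reader might expect sites to apply different scales. Section 7.0 describes recruitment through one disease team's clinics, so any inconsistency would be between assessors.
- A reader might infer that the plan misdescribes its cohort as ECOG 0-1. The summary, design and biostatistics sections make no such statement.

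**Conclusion.** The point holds as an inconsistency in how the safety population is defined. Established from the documents: either limit suffices, either scale may be recorded, nothing reconciles them, and patients admitted by either route count at 3, 6 and all 11. Resting on an assumption: that Karnofsky 60 lies below ECOG 1, which is the usual reading.

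No alpha, power or sample-size figure needs correcting. The size of any effect on the DLT count is unknown; the table shows only what follows if the rates differ. It would be wrong to conclude that patients below ECOG 1 will enrol, or that false halting is raised by a particular amount. This is a cheap improvement, not a flaw in the design's arithmetic.

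**What to change.** Reconcile the two limits. One way is to score eligibility on ECOG only in Section 6.2 and name that scale in Section 8.1. The other, if Karnofsky is kept, is to print the intended conversion and set the Karnofsky limit from it, so that both limits describe the same population.

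Raising the Karnofsky figure without a printed conversion would not settle the matter. A limit of 70 agrees with ECOG 0-1 under the 70-80 pairing, but under the 80-90 pairing a score of 70 still lies below ECOG 1.

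The cost is a few words in 6.2 and 8.1. The downside is that a patient with Karnofsky 60 may no longer be able to enter through the second scale.
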